8.3 Known AE List

Expected AEs are those AEs, the specificity and severity of which is consistent with the listings for valproic acid, sorafenib or sildenafil in Section [9](#) or those documented in the informed consent document.

8.4 Time Period and Grade of AE Capture

All AEs, regardless of grade, will be recorded from the beginning of the study procedures through 30 days following the end of the study treatment.

8.5 Procedures for Recording AEs, SAEs, Qualifying Toxicities, and UPs

All AEs, SAEs, qualifying toxicities, and UPs will be recorded in MCC's OnCore database program.

In certain instances, it may be acceptable to record in OnCore only the highest grade of a toxicity occurring during a particular study segment when an event has serial fluctuations in grade over time.

SAE's will be entered into the OnCore SAE domain. UPs will be entered into the OnCore Deviations domain. An SAE that is both an SAE and a UP will be entered in both domains. For all SAEs, a corresponding entry should be made in the routine AE record to match the event entries in the SAE domain.

8.6 Expedited Reporting Procedures for SAEs, UPs, and Qualifying Toxicities

Table 5. Expedited Reporting Requirements (Events, Report Recipients, and Time Frames)

SAEs	UPs	Qualifying Toxicities ¹
Principal Investigator, Co-Investigator (as listed below), and Coordinating Study Team ^{2, 3}	Principal Investigator, Co-Investigator (as listed below), and Coordinating Study Team ^{2, 3}	Principal Investigator, Co-Investigator (as listed below), and Coordinating Study Team ²
	DSMC ⁴	DSMC ⁴
	IRB ⁵	

¹ See Section 6.4.2.
 
² Report event within 1 business day of becoming aware of the occurrence.
 
³ A de-identified PDF of an OnCore SAE or deviation record may be used for expedited reporting purposes.
 
⁴ Report event within 2 business days of becoming aware of the occurrence. A de-identified PDF of an OnCore SAE or deviation record may be used for expedited reporting purposes.
 
⁵ Each UP must be reported to the VCU IRB within 5 business days of becoming aware of the occurrence.
		
Principal Investigator: [name] [REDACTED] [REDACTED]	[REDACTED] [REDACTED] [REDACTED] [REDACTED]	
Coordinating Study Team: [REDACTED] [REDACTED]	Massey Cancer Center DSMC: [REDACTED]	

9 PHARMACEUTICAL INFORMATION

[REDACTED]

[REDACTED]

[REDACTED]

[REDACTED]

[REDACTED]

[REDACTED]

[REDACTED]

[REDACTED]

[REDACTED]

[REDACTED]

[REDACTED]

[REDACTED]

[REDACTED]

[REDACTED]

[REDACTED]

[REDACTED]

[Redacted]

[Redacted]

[Redacted]

[Redacted]

[Redacted]

[Redacted]

[Redacted]

[Redacted]

[Redacted]

[Redacted]

[Redacted]

[Redacted]

[Redacted]

[Redacted]

[Redacted]

[Redacted]

[Redacted text block 1]

[Redacted text block 2]

[Redacted text block 3]

[Redacted text block 4]

[Redacted text block 5]

[Redacted text block 6]

[Redacted text block 7]

[Redacted text block]

[Redacted text block]

[Redacted text block]

[Redacted text block]

[Redacted text block]

[Redacted text block]

[Redacted text block]

[Redacted text block]

[Redacted text block]

[Redacted text block]

[Redacted text block]

[Redacted text block]

[Redacted text block]

[Redacted text block]

[Redacted text block]

[Redacted text block]

[Redacted text block]

[Redacted text block]

[Redacted text block]

[Redacted text block]

[Redacted text block]

[Redacted text block]

[Redacted text block]

[Redacted text block]

[Redacted text block]

[Redacted text block]

[Redacted text block]

[Redacted text block]

[Redacted text block]

[Redacted text block]

[Redacted text block]

[Redacted text block]

[Redacted text block]

[Redacted text block]

[Redacted text block]

[Redacted text block]

■ [Redacted]

[Redacted]
[Redacted]

■ [Redacted]

[Redacted]
[Redacted]

[Redacted]

[Redacted]
[Redacted]

[Redacted]

[Redacted]
[Redacted]
[Redacted]
[Redacted]

■ [Redacted]

[Redacted]
[Redacted]
[Redacted] [Redacted]
[Redacted]
[Redacted]
[Redacted]

[Redacted]
[Redacted]

■ [Redacted]

[Redacted]
[Redacted]
[Redacted]
[Redacted]

■ [Redacted]

[Redacted]
[Redacted]
[Redacted]
[Redacted]
[Redacted]
[Redacted]

[Redacted]

[Redacted]

[Redacted]

[Redacted]

[Redacted]

[Redacted]

[Redacted]

[REDACTED]

[REDACTED]

[REDACTED]

[REDACTED]

[REDACTED]

[REDACTED]

[REDACTED]

[REDACTED]

[REDACTED]

[REDACTED]

[REDACTED]

[REDACTED]

[REDACTED]

[REDACTED]

[REDACTED]	[REDACTED]	[REDACTED]
[REDACTED]	[REDACTED]	[REDACTED]
[REDACTED]	[REDACTED]	[REDACTED]
[REDACTED]	[REDACTED]	[REDACTED]
[REDACTED]	[REDACTED]	[REDACTED]
[REDACTED]	[REDACTED]	[REDACTED]
[REDACTED]	[REDACTED]	[REDACTED]
[REDACTED]	[REDACTED]	[REDACTED]
[REDACTED]	[REDACTED]	[REDACTED]
[REDACTED]	[REDACTED]	[REDACTED]
[REDACTED]	[REDACTED]	[REDACTED]
[REDACTED]	[REDACTED]	[REDACTED]
[REDACTED]	[REDACTED]	[REDACTED]
[REDACTED]	[REDACTED]	[REDACTED]
[REDACTED]	[REDACTED]	[REDACTED]
[REDACTED]	[REDACTED]	[REDACTED]
[REDACTED]	[REDACTED]	[REDACTED]
[REDACTED]	[REDACTED]	[REDACTED]
[REDACTED]	[REDACTED]	[REDACTED]
[REDACTED]	[REDACTED]	[REDACTED]
[REDACTED]	[REDACTED]	[REDACTED]
[REDACTED]	[REDACTED]	[REDACTED]
[REDACTED]	[REDACTED]	[REDACTED]
[REDACTED]	[REDACTED]	[REDACTED]
[REDACTED]	[REDACTED]	[REDACTED]
[REDACTED]	[REDACTED]	[REDACTED]
[REDACTED]	[REDACTED]	[REDACTED]
[REDACTED]	[REDACTED]	[REDACTED]
[REDACTED]	[REDACTED]	[REDACTED]
[REDACTED]	[REDACTED]	[REDACTED]

[REDACTED]

[REDACTED]

[REDACTED]

[REDACTED]

[REDACTED]

[REDACTED]

[REDACTED]

[Redacted text block]

[Redacted text block]

[Redacted text block]

[Redacted text block]

[Redacted text block]

[Redacted text block]

[Redacted text block]

[REDACTED]

[REDACTED]

[REDACTED]

[REDACTED]

[REDACTED]

[REDACTED]

[REDACTED]

[Redacted text block]

[Redacted text]

[Redacted text line]

[Redacted text]

[Redacted text line]

[Redacted text]

[Redacted text block]

[Redacted text block]

[Redacted text block]

[Redacted]

[Redacted]

[Redacted]

[Redacted]

[Redacted]

[Redacted]

[Redacted]

[Redacted]

[Redacted]

[Redacted text block]

[Redacted text block]

[Redacted text block]

[Redacted text block]

[Redacted text block]

[Redacted text block]

[Redacted text block]

[Redacted text block]

[Redacted text block]

[Redacted text block]

[Redacted text block]

[Redacted text block]

[Redacted text block]

[Redacted]	[Redacted]	[Redacted]	[Redacted]	[Redacted]
[Redacted]	[Redacted]	[Redacted]	[Redacted]	[Redacted]
[Redacted]	[Redacted]	[Redacted]	[Redacted]	[Redacted]
[Redacted]	[Redacted]	[Redacted]	[Redacted]	[Redacted]
[Redacted]	[Redacted]	[Redacted]	[Redacted]	[Redacted]
[Redacted]	[Redacted]	[Redacted]	[Redacted]	[Redacted]
[Redacted]	[Redacted]	[Redacted]	[Redacted]	[Redacted]
[Redacted]	[Redacted]	[Redacted]	[Redacted]	[Redacted]
[Redacted]	[Redacted]	[Redacted]	[Redacted]	[Redacted]
[Redacted]	[Redacted]	[Redacted]	[Redacted]	[Redacted]
[Redacted]	[Redacted]	[Redacted]	[Redacted]	[Redacted]
[Redacted]	[Redacted]	[Redacted]	[Redacted]	[Redacted]
[Redacted]	[Redacted]	[Redacted]	[Redacted]	[Redacted]
[Redacted]	[Redacted]	[Redacted]	[Redacted]	[Redacted]

[Redacted text block]

[Redacted text block]

[Redacted text block]

[Redacted]	[Redacted]	[Redacted]
[Redacted]	[Redacted]	[Redacted]
[Redacted]	[Redacted]	[Redacted]
[Redacted]	[Redacted]	[Redacted]
[Redacted]	[Redacted]	[Redacted]
[Redacted]	[Redacted]	[Redacted]
[Redacted]	[Redacted]	[Redacted]
[Redacted]	[Redacted]	[Redacted]
[Redacted]	[Redacted]	[Redacted]
[Redacted]	[Redacted]	[Redacted]
[Redacted]	[Redacted]	[Redacted]

[Redacted text block]

[Redacted text block]

[Redacted]

[Redacted]

[Redacted]

[Redacted]

[Redacted]

[Redacted]

[Redacted]

[Redacted]

[Redacted]

[REDACTED]

[REDACTED]

[REDACTED]

[REDACTED]

10 MEASUREMENT OF EFFECT

10.1 Definitions

Evaluable for toxicity. All patients will be evaluable for toxicity from the time of their first treatment with sorafenib and/or valproic acid and/or sildenafil.

Evaluable for qualifying toxicities for the safety lead-in. Only those patients who have completed the first cycle of therapy (or have experienced a qualifying toxicity prior to the end of the first cycle) will be evaluable for the safety lead-in. Qualifying toxicities will be defined in the first cycle only. Patients must have completed twice-daily sorafenib dosing for at least 21 out of the first 28 days to be considered to have had sufficient exposure to the regimen for qualifying toxicity evaluation. Patients who are not evaluable for the qualifying toxicity assessment for the safety lead-in will be replaced.

Evaluable for qualifying toxicities for the early stopping rule after the safety lead-in. Patients who have initiated the first cycle of therapy will be considered evaluable for the early stopping rule. Qualifying toxicities will be defined in the first cycle only. Patients who are not evaluable for the qualifying toxicity assessment for the early stopping rule will not be replaced unless they were included in the safety-lead in.

Evaluable for objective response. Patients who have been treated with the combination of twice-daily sorafenib and valproic acid for a minimum of 28 days, and have had their disease re-evaluated, will be considered evaluable for response. These patients will have their response classified according to the definitions stated below. Patients who do not complete study dosing for at least 28 days, or those who do not have their disease re-evaluated following initiation of the combination of sorafenib and valproic acid, will be replaced to ensure that a sufficient number of patients will be available for response evaluation.

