6.2 Schedule

The treatment schedule is combined sorafenib, valproic acid, and sildenafil, administered orally, twice daily continuously. A cycle consists of 4 weeks. The first cycle begins once therapy begins with all 3 agents—after, if necessary, titration of valproic acid dosage, described in Section [6.2.7](#). Titration of valproic acid may occur as a matter of clinical preference, prior to study enrollment.

Study drug therapy is taken on an empty stomach, that is, at least 1 hour before or 2 hours after eating, due to absorption characteristics of sorafenib.

The first 6 patients evaluable for qualifying toxicity assessment will be treated as a safety lead-in; enrollment will be gated (the first 3 evaluable patients must complete 4 weeks of the combination therapy before the next 3 patients start combination treatment on protocol) and patients will undergo weekly evaluations for qualifying toxicities (Section [6.4.2](#)) during the first 4 weeks of combination therapy.

- 6.2.1 Initiation of sorafenib and sildenafil will not take place until valproic acid levels are \geq LLN for the laboratory, which generally takes 5-7 days after initiation.
- 6.2.2 Valproic acid will be administered orally, generally twice daily. The tablets or capsules should be swallowed without chewing to avoid local irritation of the mouth and throat. Patients who experience gastrointestinal irritation may benefit from administration of the drug with food or by slowly building up the dose from an initial low level.
- 6.2.3 If a patient is already on valproic acid and blood levels are \geq LLN for the laboratory, no further titration is necessary.
- 6.2.4 If a patient presents for evaluation for this study and are at risk for seizures, the patient may be started on valproic acid.
- 6.2.5 If a patient is already on non-valproic acid antiepileptic therapy, they may be transitioned to valproic acid, as a matter of clinical preference, prior to enrollment to obtain levels \geq LLN for the laboratory prior to discontinuing the original antiepileptic therapy.
- 6.2.6 Patients with disease recurrence require routine maintenance on antiepileptic therapy. If a patient presents for study evaluation before initiation of antiepileptic

medication, patient may start valproic acid titration to \geq LLN for the laboratory as a matter of clinical care.

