6.4.2 Qualifying Toxicities for the Safety Lead-In and Safety Stopping Rule

Qualifying toxicities for the safety lead-in are evaluated weekly during the first 4 weeks of combination treatment for each of the first 6 patients deemed evaluable for qualifying toxicity for the safety lead-in (see Section [10.1](#)).

Qualifying toxicities for the safety stopping rule are evaluated regularly during the first 4-week cycle of combination treatment for patients deemed evaluable for the early stopping rule (see Section [10.1](#)).

Qualifying toxicities are defined as any of the following that are possibly, probably, or definitely related to drug therapy:

Any grade \geq 3 toxicity, except the following:

- nausea, vomiting, or diarrhea in the absence of adequate prophylaxis and/or responsive to medical management
- grade 3 thromboembolic event

- grade 3 hyperglycemia
- grade 3 PPE (hand-foot syndrome)
- fatigue responsive to medical management
- grade 3 hypertension
- electrolyte abnormalities that, once corrected, can be maintained with oral repletion
- grade 3 anemia, platelets, neutrophils, WBC, lymphocytes, febrile neutropenia

6.4.3 See Section [8.5](#) for AE and qualifying toxicity reporting procedures.

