13.6.2 Sequential Safety Stopping Rule after the Safety Lead-in

In addition to the safety lead-in described above, a formal sequential stopping guideline, which is based on the occurrence rate of qualifying toxicities, is designed for a phase 2 study, with a relatively looser threshold than the safety lead-in rule. If the stopping guideline is reached, accrual is stopped and a thorough review of the safety data is completed by the DSMC. The stopping guideline indicates a level of concern based on the occurrence rate of qualifying toxicities. However, the stopping guideline is not an indicator that an insurmountable safety problem exists. Likewise, the fact that a stopping guideline is not reached does not provide assurance that the drug combination is safe. Qualifying toxicity is defined in Section [6.4.2](#).

Previous studies of sorafenib have shown the acceptable occurrence rate for grade 3 or greater toxicities is $\leq 35\%$ ([41](#)). Using a binomial probability calculation, values of “m” (number of patients with qualifying toxicities) and “n” (number of qualifying toxicity-evaluable patients that have been treated) are selected such that the two-sided 95% confidence interval of the sequential observed occurrence toxicity rate keeps containing the prefixed acceptable occurrence rate $\leq 35\%$.

More specifically, the following values of m/n apply to those patients who are qualifying toxicity evaluable: 5/7, 6/8-9, 7/10-11, 8/12-13, 9/14-15, 10/16-17, 11/18-19, 12/20-21, 13/22-23, 14/24-25, 15/26-28, 16/29-30, 17/31-32, 18/33-34, 19/35-37, 20/38-39, 21/40-41, 22/42-44, 23/45-46, 24/47-48, 25/49-51, 26/52-53, 27/54-56, 28/57-58, 29/59-61, 30/62-63, 31/64-65, 32/66. If, at any time, m/n reaches the values shown, accrual to the study protocol is stopped and the accumulated safety data is submitted to the DSMC for evaluation. Please refer to Section [6.4.2](#) for a list of qualifying toxicities.

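### The stopping-rule denominator takes in patients on day 1 of cycle 1 with no exposure minimum, so event-free early leavers stay in it and weaken the rule

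*Combined protocol and SAP*

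**What the plan says.** Section 13.6.2 compares m, the number of patients with qualifying toxicities, with a listed boundary at n, the "number of qualifying toxicity-evaluable patients that have been treated". The comparison can be made at any time, and reaching the boundary stops accrual for DSMC review. Table 16 in Section 13.6.3 makes the count cumulative, so the six lead-in patients are in it.

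Section 10.1 defines who is evaluable for this rule: "Patients who have initiated the first cycle of therapy will be considered evaluable for the early stopping rule". Section 6.2 fixes that moment: "The first cycle begins once therapy begins with all 3 agents". Valproic acid titration beforehand does not count. For the numerator, Section 6.4.2 says "Qualifying toxicities for the safety stopping rule are evaluated regularly during the first 4-week cycle of combination treatment".

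For the same event in the lead-in, Section 10.1 is stricter. It admits "Only those patients who have completed the first cycle of therapy", or those with a qualifying toxicity before the cycle ends, and adds "Patients must have completed twice-daily sorafenib dosing for at least 21 out of the first 28 days". No section sets a closed window or an exposure minimum for the later rule. Section 10.1 also says that patients not evaluable for the later rule are generally not replaced, but under its own definition almost no treated patient could fall in that group.

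**The concern.** The rule compares a four-week event rate with 35%. That comparison is fair only if each patient in n has had a reasonable chance to contribute to m. Two groups have not.

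- **New starters** are in n before their window has run. This corrects itself within 28 days.
- **Early leavers without an event**, for example after progression or withdrawal in the first weeks, stay in n permanently as toxicity-free.

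Section 10.1 foresees such leavers: patients who do not complete 28 days of dosing are replaced for response. The leaver stays in the safety denominator while the replacement is added to it. Because the boundary rises with n, a regimen with too much toxicity in adequately exposed patients is less likely to trigger the review.

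**Working it through.** **Inputs.** Boundary list from 5/7 to 32/66, two-sided 95% interval, reference rate 35% (13.6.2). Lead-in passed with at most 1 of 6 (13.6.1). Accrual 8-12 per year, expected total 44, maximum 66 (13.1, 13.2). The early-leaver share u is not in the documents; 10-20% is assumed, with 0-30% as the range. True rates of 50% and 35% are scenarios.

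**1. The plan's boundary.** Take the smallest m with m/n − 1.96·√[(m/n)(1 − m/n)/n] > 0.35. This normal-approximation interval reproduces all 60 listed values, so the list agrees with its inputs.

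**2. Effect of one uninformative patient.**
- 9/15: 0.600 − 1.96·√(0.24/15) = 0.352, above 0.35, so accrual stops.
- 9/16: 0.5625 − 1.96·√(0.2461/16) = 0.319, so accrual continues; the boundary is 10.

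This shows the mechanism and is not a likely path. Over the whole list, a just-met boundary is undone by one added event-free patient at 27 of 59 values of n, by two at 52 of 58, and by three at 57 of 57.

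**3. New starters.** The mean number of open windows is 8 × 28/365 = 0.61 to 12 × 28/365 = 0.92. A simulation (Poisson accrual, toxicity time uniform over 28 days, continuous checking, 6,000 runs per scenario) puts the loss in the chance of stopping at about 0-4 points.

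**4. Early leavers.** An exact recursion over (n, m) starts from 0 or 1 event in 6, given a passed lead-in. At a true rate p = 0.50 these have probabilities 1/7 and 6/7. A further 38 patients are treated, 44 in all. Leaving and toxicity times are uniform over 28 days, so a leaver carries half the risk; events after leaving are not counted. For each patient:
- event: p(1 − u/2), counted in m and n under both definitions;
- event-free completer: (1 − p)(1 − u), counted in n under both;
- event-free leaver: u(1 − p/2), counted in n as written, left out under the lead-in-style definition.

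At u = 0.20 these are 0.45, 0.40 and 0.15.

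| Leavers | As written | Lead-in-style |
|---|---|---|
| none | 36% | 36% |
| 10%, leaving uniformly | 26% | 36% |
| 20%, leaving uniformly | 17% | 39% |
| 10%, no risk at all | 17% | 30% |
| 20%, no risk at all | 6% | 25% |

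In the no-risk rows the event probability is p(1 − u). The simulation in step 3, which includes new starters at 10 per year, gives 24% against 36% and 17% against 40% for the two uniform rows.

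The lead-in-style column drops every event-free leaver. If those who leave event-free after day 21 are kept, u/4 × (1 − p × 24.5/28) moves back into n, and the corrected figures become about 34% at both leaver rates.

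**5. Price at the acceptable rate.** Dropping leavers without events while keeping those with events biases the counted rate upward: at u = 0.20, 0.45/(0.45 + 0.40) = 53% against a true 50%. As written the expected rate is 45%. At a true 35% rate and N = 66, the chance of a stop under the lead-in-style definition is about 2.5% with no leavers, 3.5% at 10%, 5% at 20% and 6.5-7.5% at 30%.

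**The case against.** Counting everyone who starts treatment is a recognised safety denominator, and Section 10.1 defines the two populations separately and on purpose. Section 13.6.2 describes the later rule as looser than the lead-in and warns that not reaching it is no assurance of safety. That defends a looser threshold. It does not explain why the exposure called sufficient for judging this event in the first six patients is not needed afterwards, when both groups enter one cumulative m/n.

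Early leavers are also not lost to observation. Section 7.8 keeps most of them in a 30-day adverse-event period, and Section 8.4 records events for that long. This stands: they can still contribute events before leaving, and possibly after it. What is cut short is their exposure, so treating them as carrying no risk is an extreme case.

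A reader might infer that this rule is the only toxicity monitor after the sixth patient. The documents do not support that. Qualifying toxicities go to the DSMC within 2 business days (Table 5), the study team meets at least monthly and considers further enrollment (14.1), and the DSMC reviews on its own schedule (14.2.2).

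The leaver rate is assumed. Routine imaging is every 8 weeks (10.4), so scheduled scans would not take patients off treatment within cycle 1.

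**Conclusion.** The point holds as a weakness in the denominator's definition and should be corrected. Under uniform leaving at 10-20%, a true 50% rate, a passed lead-in and 44 treated, the plan's wording lowers the chance of reaching the boundary by about 10 points (26% against 36%) to 22 points (17% against 39%). With event-free leavers after day 21 kept in n, the gap is about 8 to 17 points. With no early leavers, only the small new-starter effect remains.

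Two stronger readings should be resisted. One is that the denominator alone takes the chance of stopping from 36% to 6%. That gives leavers no risk at all, and part of the fall is simply fewer informative patients: under the same assumption the corrected rule reaches only 25%. The other is that new starters are a main cause; at the planned accrual they are a small and temporary one. Section 13.2 mentions adding sites but gives no accrual figure that would change this.

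**What to change.** In Sections 10.1 and 13.6.2, count a patient in n once he or she has had a qualifying toxicity or has completed the 28-day window. Leave out event-free patients who stopped before the lead-in's exposure minimum for reasons other than toxicity. Patients who stopped because of toxicity stay in. State separately how open windows and early leavers are handled, and whether events after leaving but within 28 days count.

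The data are already collected, but the change is not free. The denominator lags enrollment by up to 4 weeks. The observed rate is biased slightly upward, both by dropping event-free leavers and because events enter at once while event-free patients wait. Stops at the acceptable rate become modestly more frequent, as in step 5. A stop pauses accrual for DSMC review, so this is a small price, but the operating characteristics should be reported with the revised rule.

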3.2 Primary Endpoint

Proportion of patients evaluable for response, regardless of tumor PDGFR status, with 6-month PFS defined as the time from the first day a patient receives study treatment until time of progression per RANO or Macdonald criteria or death, whichever occurs first.

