10.4 Timing of Imaging Studies

For the purposes of this study, patients will be re-evaluated for response every 8 weeks. In addition to a baseline scan, confirmatory scans should also be obtained 4 weeks following initial documentation of objective response (PR or CR).

Evaluation of neurologic imaging can be confounded by factors such as edema and subtle variances in imaging parameters. In the event that imaging meets objective progression criteria, but the patient's clinical status is stable or improving, with a stable or decreasing steroid dose, and, in the opinion of the investigator, the aggregate patient assessment is not definitive for progression, study therapy can continue at investigator's discretion with repeat imaging at time of next scheduled assessment. If subsequent imaging again meets objective progression criteria, regardless of clinical and/or steroid dosing status, then progression criteria will have been met, and the date of progression will be noted as the earliest imaging date that was consistent with objective progression.

If clinical conditions raise the concern for progressive disease in between regularly scheduled interval scans, repeat imaging may be performed at the treating physician's discretion.

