10.4.2 PFS

PFS is defined as the duration of time from start of treatment to time of symptomatic and/or radiographic progression or death, whichever occurs first.

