- E. If baseline history and physical exam is performed on a day other than C1D1, a brief visit to determine neurologic stability on current dose of steroids is also required on day 1 or day before.
- F. Only patients in the safety lead-in cohort.
- G. For women capable of pregnancy: pregnancy test at baseline; subsequently, review pregnancy risks and offer pregnancy test
- H. First “on-treatment” ECG is done approximately C1D8-C1D15 to evaluate acute changes relative to the study drug combination; the second is done approximately C3D1 to evaluate changes after a more chronic dosing of study drug combination.
- I. MRI or contrast-enhanced CT within 3 weeks prior to enrollment. An MRI is the preferred modality in all patients without a contraindication to MRI. Baseline and follow-up scans must be performed using the same modality.
- J. Imaging to be done to assess response every 2 months from initiation of treatment until off-study due to patient withdrawal, progression, or death. If MRI or contrast-enhanced CT shows response then repeat after 1 month to confirm response and then follow every 2 months from time of confirmatory MRI or CT. Patients with symptoms suggestive of progression may have imaging done between regularly scheduled scans, any time there is clinical concern for progressive disease. See also Section [10.4](#).
- K. See Section [7.8](#): After stopping study treatment, capture initiation of new therapy, first new progression date, and/or survival status since last observation approximately every 2 months during extended follow-up.
- L. Obtain and analyze archived tumor tissue per Section [11](#). During enrollment of the initial PDGFR α -unselected subgroup (prior to first interim analysis), archived tumor tissue must be obtained and analyzed, but analysis does not need to be performed prior to enrollment. After the first interim analysis, if the study proceeds to include only PDGFR α -positive patients, archived specimen analysis for PDGFR α will be required, and results must be known, prior to enrollment.
- M. Sodium, potassium, carbonate, chloride, glucose, calcium, BUN, creatinine.
- N. Additional assessments may be done at investigator discretion in patients with congestive heart failure, bradyarrhythmias, those on drugs known to prolong the QT interval, including Class Ia and III antiarrhythmics, and electrolyte abnormalities.
- O. ALT, AST, ALP, total bilirubin, direct bilirubin, albumin, total protein.

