13.2 Sample Size/Accrual Rates

The sample size and power are calculated based on Simon's two-stage mini-max design which minimizes the expected maximum sample size ([35](#)). The primary outcome, 6-month PFS, is considered as a binary variable, ie, a patient either has 6-month PFS or not. Per the previous studies of second-line therapy in GBM, we assume that the null hypothesis, the proportion of patients who have 6-month PFS, is $\leq 20\%$, ie, $p_0 \leq 0.2$, which is unacceptably low, and the true proportion is $p_1 = 0.4$. With a one-sided type I error of 5% and power of at least 80%, the first stage will enroll 16 response-evaluable patients. If there are 3 or less response-evaluable patients who have 6-month PFS, then the trial in the unselected patient population will end. If 4 or more response-evaluable patients have 6-month PFS, then the trial will enroll an additional 17 response-evaluable patients into the second stage. If 11 or more out of the total of 33 response-evaluable patients have 6-

month PFS, the drug combination meets efficacy criteria and further studies can be pursued.

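### The primary 6-month PFS proportion drops and replaces patients who stop dosing before day 28 or are not re-evaluated, even when the reason is early death or progression

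*Combined protocol and SAP*

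**What the plan says.** Section 3.2 defines the primary endpoint as "Proportion of patients evaluable for response, regardless of tumor PDGFR status, with 6-month PFS". Section 13.4 analyses it in the same set, and section 13.2 writes both cut-offs (at least 4 of 16, then at least 11 of 33) for response-evaluable patients. A second Simon design for PDGFRα-positive patients would use the same settings.

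Section 10.1 defines that set as "Patients who have been treated with the combination of twice-daily sorafenib and valproic acid for a minimum of 28 days" whose disease has also been re-evaluated. It replaces "Patients who do not complete study dosing for at least 28 days, or those who do not have their disease re-evaluated following initiation" of the two-drug combination. No reason for stopping is exempt. In the same section, the safety lead-in definition does carry an exception: patients who complete cycle 1 are evaluable, "or have experienced a qualifying toxicity prior to the end of the first cycle".

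Section 10.4.2 runs PFS "from start of treatment to time of symptomatic and/or radiographic progression or death, whichever occurs first". Under section 7.6, progression ends study treatment. On scans, section 10.4 says "patients will be re-evaluated for response every 8 weeks". Section 7.8 takes patients who are not response-evaluable off study after the initial 30-day adverse-event period.

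The null is introduced in section 13.2 as follows: "Per the previous studies of second-line therapy in GBM, we assume that the null hypothesis, the proportion of patients who have 6-month PFS" is at most 20%. The alternative is 40%. The section does not say whether these rates refer to all treated patients or only to evaluable ones.

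**The concern.** Death and progression are PFS events from the first day of treatment, and neither needs 28 days of dosing to be known. Yet a patient who dies before day 28, or progresses and stops treatment before then, fails the evaluability test and is replaced. Each such replacement removes a known failure and adds a new chance of success.

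The term re-evaluated is not defined. If it means imaging, a patient who dies between day 28 and the first scheduled scan at week 8, with no earlier scan, is replaced as well.

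Both decisions rest on this set. The 4/16 look decides whether accrual stays unselected or narrows to PDGFRα-positive tumors, and the 11/33 look declares efficacy. Section 7.8 also means that later progression and survival are not collected for patients who stop early for other reasons, so a complete all-treated analysis could not be assembled afterwards.

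**Working it through.** **Inputs from section 13.2.** Null 0.20, alternative 0.40; continue if at least 4/16 succeed; declare efficacy if at least 11/33 succeed.

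**Step 1: reproduce the plan.** With true rate p in the analysed set,

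P(efficacy | p) = Σ over x = 4 to 16 of P[Bin(16, p) = x] × P[Bin(17, p) ≥ 11 − x].

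This gives 0.0475 at p = 0.20 and 0.811 at p = 0.40, so the first Simon design meets its stated 5% and 80%. The chance of passing stage 1 at the null, P[Bin(16, 0.20) ≥ 4], is 0.402. Alpha reaches 5% at p = 0.2016, so there is little slack.

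**Step 2: effect of replacement.** Suppose the rate in all treated patients is 0.20, a share e is replaced, and the replaced patients' own 6-month PFS rate is s. The rate in the evaluable set is then

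p_eval = (0.20 − e·s) / (1 − e).

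The documents give neither e nor s; both are assumptions here. For e = 10% and s = 0: 0.20/0.90 = 0.2222.

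| Share replaced | p_eval, s = 0 | alpha, s = 0 | pass stage 1, s = 0 | p_eval, s = 0.1 | alpha, s = 0.1 |
|---|---|---|---|---|---|
| 5% | 0.2105 | 6.5% | 44.4% | 0.2053 | 5.6% |
| 10% | 0.2222 | 9.0% | 49.0% | 0.2111 | 6.7% |
| 15% | 0.2353 | 12.4% | 54.1% | 0.2176 | 8.0% |
| 20% | 0.2500 | 17.1% | 59.5% | 0.2250 | 9.7% |

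If s = 0.20, p_eval stays at 0.20 and alpha at 4.75%. With s = 0, alpha passes 5% once e exceeds about 0.8%, since 1 − 0.20/0.2016 = 0.008.

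**Step 3: in counts of patients.** With k replaced failures alongside 33 evaluable patients, e = k/(33 + k).
- k = 1: e = 1/34 = 2.9%, alpha 5.7%.
- k = 4: e = 4/37 = 10.8%, alpha 9.5%. A bare success of 11/33 = 33.3% is 11/37 = 29.7% of treated patients.

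**Step 4: a rough scale for early deaths.** Section 1.1 gives median survival after recurrence of 25 to 30 weeks (grade IV) and 39 to 47 weeks (grade III). Under an assumed constant hazard, deaths by week 4 are 1 − 2^(−4/m) for median m. For m = 25, 30, 39 and 47 weeks this is 10.5, 8.8, 6.9 and 5.7%. Halving the early hazard, because eligible patients may be fitter, gives 5.4, 4.5, 3.5 and 2.9%. If only these deaths were replaced, alpha would be 6.9 to 9.3% at the full hazard and 5.7 to 6.7% at half.

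**The case against.** The strongest reply is that the rule is written throughout for response-evaluable patients, so 20% and 40% may have been meant for that set. Alpha and power are then as stated and the design contains no arithmetic error. This stands as far as error rates go. It does not rescue the estimate, which would describe patients who survived and stayed on treatment for 28 days, not patients who were treated.

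The size is also uncertain. No replacement rate is given, the 15% and 20% rows have no source in the documents, and treating every replaced patient as a failure is the worst case. Some will stop for toxicity or withdraw, with unknown 6-month status. Eligibility requires ECOG 0 to 2 and fixed or falling steroids, so early deaths may be fewer than the medians suggest. All of this is fair, and the lower range from step 4 is the safer guide to scale.

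Other defences are weaker. Section 13.7 codes non-evaluable patients as non-responders, but only for complete or partial response. The Kaplan-Meier curves in 13.4 and 13.5 for the entire population may only be a contrast with the PDGFRα subgroup, and they do not drive the decision rules. Deaths before day 28 would be known from adverse-event follow-up; that makes them easy to count but does not put them in the denominator.

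The gap has limits. A patient who takes 28 days of dosing and progresses at the week-8 scan stays in as a failure. The sequential toxicity rule after the lead-in counts everyone who starts cycle 1 and is unaffected.

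**Conclusion.** The concern holds, and the definition is wrong as written for a PFS endpoint. Certain early failures leave the primary denominator and are replaced, so the proportion is biased upward for treated patients to the extent that replaced patients do worse. There is no bias if they do as well as the rest.

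The effect on alpha depends on the null describing all treated patients. On that reading, a single replaced failure takes alpha from 4.75% to 5.7%, and early deaths on the scale of section 1.1 take it to between 5.7% and 9.3%. If the null describes evaluable patients, alpha is unchanged but the conclusion applies only to them. The direction of the problem is clear from the text; its size rests on assumed replacement rates. It must be fixed because both go/no-go decisions depend on it and section 7.8 prevents full repair later.

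**What to change.** **Primary set.** In 3.2, 3.3, 10.1 and 13.2 to 13.5, define it as all eligible patients who start the three-drug combination at the dose carried into expansion, with no replacement for efficacy. If the lead-in results in a dose change, report patients on the abandoned dose separately. Apply the 16/33 cut-offs to this set in each Simon design, state that 20% and 40% refer to it, and keep the response-evaluable set as supportive.

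**Failure rule.** Count progression, death, or no documented progression-free status at 6 months as failure, within a stated assessment window. On an 8-week schedule the third scan falls at week 24, about 2 weeks before 6 months (182.6/7 = 26.1 weeks), and the next at week 32. The calendar says "Imaging to be done to assess response every 2 months from initiation of treatment", so the two schedules need aligning.

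**Follow-up and wording.** Change 7.8 so that all treated patients are followed for progression and survival. Define re-evaluated. Reconcile replacement in 10.1 with the coding in 13.7, and the twice-daily condition in the 10.1 evaluability sentence with the dose steps in 7.1.

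**Cost.** Wording, a few more follow-up contacts and a less favourable estimate. If 40% applies to all treated patients under this failure rule, alpha 4.75% and power 81.1% hold for the first Simon design taken alone, with no extra patients. Error across the two designs combined is a separate matter.

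If 40% was meant for evaluable patients, the treated rate is 0.40(1 − e) + e·s and power must be restated. At 5, 10, 15 or 20% excluded it is 74, 66, 57 or 48% with s = 0, and 76, 71, 64 or 57% with s = 0.1. Restoring 80% would need a maximum of about 40 or 49 treated patients per Simon design at 5 or 10% excluded (s = 0). Likewise, if 5 or 10% of true successes lack a documented 6-month status, the rate falls to 0.38 or 0.36 and power to 74 or 66%, so the window should be set to keep such losses rare.
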